2.8.2 Deaths

Separate summaries for on-treatment and all deaths including on-treatment and post-treatment deaths will be produced by system organ class and preferred term.

All deaths will be listed for the Safety set, post-treatment deaths will be flagged. A separate listing of deaths prior to starting treatment will be provided for all screened patients.

2.8.3 Laboratory data

Grade categorization of lab values will be assigned programmatically as per NCI Common Terminology Criteria for Adverse Events (CTCAE) version 4.03. The calculation of laboratory CTC grades will be based on the observed laboratory values only, clinical assessments will not be taken into account. The criteria to assign CTC grades are given in Novartis internal criteria for CTC grading of laboratory parameters. The latest available version of the document based on the underlying CTCAE version 4.03 at the time of analysis will be used.

For laboratory tests where grades are not defined by CTCAE v4.03, results will be graded by the low/normal/high (or other project-specific ranges, if more suitable) classifications based on laboratory normal ranges.

A severity grade of 0 will be assigned for all non-missing lab values not graded as 1 or higher. Grade 5 is not applicable. For laboratory tests that are graded for both low and high values, summaries will be done separately and labeled by direction, e.g., sodium will be summarized as hyponatremia and hypernatremia.

Data analysis

On analyzing laboratory, data from all sources (central and local laboratories) will be combined. The summaries will include all assessments available for the lab parameter collected no later than 30 days after the last study treatment administration date (see Section 2.1.1).

The following summaries will be produced for hematology and biochemistry laboratory data (by laboratory parameter and treatment):

- Worst post-baseline CTC grade (regardless of the baseline status). Each subject will be counted only for the worst grade observed post-baseline.
- Shift tables using CTC grades to compare baseline to the worst on-treatment value
- For laboratory tests where CTC grades are not defined, shift tables using the low/normal/high/(low and high) classification to compare baseline to the worst on-treatment value.
- Trends of lab parameter values over time (baseline and selected on-treatment timepoints) should be displayed via boxplots based on time windows and corresponding tables displaying the statistics used for the box plots by the selected time points.

The following listings will be produced for the laboratory data:

- Listings of all laboratory data, with CTC grades and classification relative to the laboratory normal range. Lab data collected during the post-treatment period will be flagged.
- Listing of all CTC grade 3 or 4 laboratory toxicities

Novartis	Confidential	Page 49
SAP	30-Sep-2021 (6:19)	CDRB436G2201

Liver function parameters

Liver function parameters of interest are total bilirubin (TBIL), ALT, AST and alkaline phosphatase (ALP). The number (%) of patients with worst post-baseline values as per Novartis Liver Toxicity guidelines will be summarized.

The following summaries will be produced:

- ALT or AST > 3xULN
- ALT or AST > 5xULN
- ALT or AST > 8xULN
- ALT or AST > 10xULN
- ALT or AST > 20xULN
- TBL > 2xULN
- TBL > 3xULN
- ALT or AST > 3xULN & TBL > 2xULN
- ALT or AST > 3xULN & TBL > 2xULN & ALP < 2xULN

Potential Hy's Law events are defined as those patients with occurrence of AST or ALT > 3xULN and TBL > 2xULN and missing ALP or ALP < 2xULN at any time during the ontreatment period. Note that the criteria relating to combined elevations of AST (or ALT) and TBL are based on the peak values at any post-baseline time for a subject.

For patients with abnormal ALT or AST baseline values, a clinically significant liver safety signal corresponding to Hy's law is defined by : [ALT or AST > 3xbaseline] OR [ALT or AST >8xULN], whichever is lower, combined with [TBIL >2xbaseline AND >2xULN].

A figure displaying time course of hepatic function tests (ALT, AST, TBL, ALP) in patients meeting Hy's criteria will be displayed in the Safety Set. Additonally, evaluation of drug-induced serious hepatotoxicity (eDISH) plots will be produced to display ALT and AST values by TBL values in units of ULN.

2.8.4 Other safety data

2.8.4.1 ECG and cardiac imaging data

ECG Data handling

In case the study requires ECG replicates at any assessment, the average of the ECG parameters at that assessment should be used in the analyses.

ECG Data analysis

Standard 12-lead ECGs including PR, QRS, QT, QTcF, and HR intervals will be obtained local for each patient during the study. ECG data will be read and interpreted locally.

Novartis	Confidential	Page 50
SAP	30-Sep-2021 (6:19)	CDRB436G2201

The number and percentage of patients with notable ECG values will be presented by treatment group:

- QT, QTcF
 - New value of > 450 and ≤ 480 ms
 - New value of > 480 and ≤ 500 ms
 - New value of > 500 ms
 - Increase from Baseline of $> 30 \text{ ms to} \le 60 \text{ms}$
 - Increase from Baseline of > 60 ms
- PR
 - Increase from baseline >25% and to a value >200 ms
 - New value of > 200 ms
- QRS
 - Increase from baseline >25% and to a value > 120 ms
 - New values of QRS > 120 ms

The normal range for HR is displayed in Table 2-14. The number and percentage of patients with notable values will be presented.

 Table 2-14
 Recommendation for normal heart rate per age group and gender

Age group	0-1 month	1-3 months	3-6 months	6-12 months	1-3 years	3-5 years	5-8 years	8-12 years	12-18 years
HR (bpm) Boys	(125, 190)	(125, 185)	(110, 165)	(105, 165)	(95, 155)	(75, 125)	(60, 115)	(55, 100)	(50, 100)
HR (bpm) Girls	(135, 215)	(125, 200)	(120, 190)	(105, 185)	(95, 180)	(80, 125)	(70, 115)	(60, 110)	(50, 100)

Data shown as upper limit of normal, lower limit of normal for HR= heart rate. Ref.: adapted from Rijnbeek et al. 2001.

The summaries will include all ECG assessments performed no later than 30 days after the last date of study drug. A listing of all ECG assessments will be produced and notable values will be flagged. A separate listing of only the patients with notable ECG values may also be produced. In the listings, the assessments collected during the post-treatment period will be flagged.

The denominator to calculate percentages for each category is the number of patients with both a baseline and a post-baseline evaluation. A newly occurring post-baseline ECG notable value is defined as a post-baseline value that meets the criterion post-baseline but did not meet the criterion at baseline.

For each ECG parameter, descriptive statistics at baseline, at each post-baseline time point and changes from baseline at each post-baseline time point will be summarized. Descriptive statistics at worst post-baseline and changes from baseline to worst post-baseline will also be summarized separately.

Novartis	Confidential	Page 51
SAP	30-Sep-2021 (6:19)	CDRB436G2201

For each of the QTc and QT intervals, shift tables based on notable parameter categories (<450, 450-<481, 481-<501, ≥501 ms) at baseline and the worst post-baseline value observed.

Frequency counts and percentages of patients with newly occurring post-baseline qualitative ECG abnormalities (morphology) will be summarized. The denominator to calculate percentages is the number of patients with both a baseline and a post-baseline evaluation. A newly occurring post-baseline qualitative ECG abnormality is defined as a post-baseline abnormal finding which was not present at baseline.

Patients with notable ECG interval values and newly occurring qualitative ECG abnormalities will be listed and the corresponding notable values and abnormality findings will be included in the listings.

Unscheduled ECG measurements will not be used in computing the descriptive statistics for change from baseline at each post-baseline time point. However, they will be used in the analysis of notable ECG changes and the shift table analysis of notable QT parameters.

ECHO Data handling

ECHO data will be analyzed based on local reported results. The summaries will include all ECHO assessments performed no later than 30 days after the last date of study drug. All ECHO assessments will be listed, and those collected later than 30 days after study drug discontinuation will be flagged in the listing.

The same modality (ECHO or MUGA) for determining cardiac scan data (e.g., left ventricular ejection fraction (LVEF)) should be used to follow a patient throughout the study. The absolute change from baseline values will not be calculated for any patients where the post-baseline value was determined by a cardiac scan modality that is different than the one used to determine baseline value.

ECHO Data analysis

Absolute change from baseline in LVEF will be summarized in the worst case post-baseline. Only the post-baseline assessments that used the same method (ECHO or MUGA) as the baseline assessments will be used to derive the change from baseline. The change from baseline will be categorized as follows:

- No change or any increase
- Any decrease:
 - \circ > 0 <10% Decrease
 - 10 <20% Decrease
 - $\circ \geq 20\%$ Decrease
- $\geq 10\%$ decrease and $\geq LLN$
- $\geq 10\%$ decrease and < LLN
- $\geq 20\%$ decrease and $\geq LLN$
- $\geq 20\%$ decrease and < LLN

Novartis	Confidential	Page 52
SAP	30-Sep-2021 (6:19)	CDRB436G2201

ECHO assessments of LVEF will be listed for each patient including absolute change from baseline at each assessed time interval. The values of potential clinical importance will also be flagged.

2.8.4.2 Vital signs

Vital sign assessments are performed in order to characterize basic body function. The following parameters are being collected: height (cm), weight (kg), body temperature (°C), pulse rate (beats per minute), systolic and diastolic blood pressure (mmHg).

Data handling

Vital signs collected on treatment will be summarized. Values measured outside of on treatment period will be flagged in the listings.

Data analysis

For analysis of vital signs the clinically notable vital sign criteria are provided in Table 2-145 below.

	Clinically notable criteria				
Vital sign (unit)	Hig	gh	Low		
Systolic blood pressure [mmHg]	≥ 95th percentile of the age and height group ¹		≤ 5th percentile of the age and height group ¹		
Diastolic blood pressure [mmHg]	≥ 95th percentile of the age and height group ¹		Sth percentile of the age height group ¹		
Body temperature [°C]	≥ 38.4°C		≤ 35.	.0°C	
Pulse rate [bpm] ²	12-18 months	> 140	12-18 months	< 103	
	18-24 months	> 135	18-24 months	< 98	
	2-3 years	> 128	2-3 years	< 92	
	3-4 years	> 123	3-4 years	< 86	
	4-6 years	> 117	4-6 years	< 81	
	6-8 years	> 111	6-8 years	< 74	
	8-12 years	> 103	8-12 years	< 67	
	12-15 years	> 96	12-15 years	< 62	
	≥ 15 years	> 92	≥ 15 years	< 58	
Weight	increase from baseline³ of ≥ 2 BMI-for-age percentile categories⁴		decrease from b BMI-for-age per categories ⁴		

Table 2-15Criteria for notably abr	normal vital signs
------------------------------------	--------------------

bpm=beats per minute; CDC= Centers for Disease Controls and prevention; NHLBI= National Heart, Lung, and Blood Institute;

¹ Blood pressure percentiles are calculated for each blood BP record using the method described in Appendix B of the following reference: The Fourth Report on Diagnosis, Evaluation and Treatment of High Blood Pressure in Children and Adolescents. Pediatrics 2004; 114; 555. Note: Methods applies to patients less than 3 years old.

Novartis	Confidential	Page 53
SAP	30-Sep-2021 (6:19)	CDRB436G2201

	Clinically notable criteria		
Vital sign (unit)	High	Low	

² Fleming S, Thompson M, Stevens R, et al. Normal ranges of heart rate and respiratory rate in children from birth to 18 years of age: a systematic review of observational studies. Lancet 2011; 377: 1011-18.

³ Baseline BMI-for-age weight status categories are underweight (less than the 5th percentile), healthy weight (5th percentile to less than the 85th percentile), overweight (85th to less than the 95th percentile) and obese (equal to or greater than the 95th percentile);

⁴ BMI-for-age percentiles categories (P3, P5, P15, P25, P50, P75, P85, P95, P97) are obtained from the WHO Growth Charts (http://www.who.int/childgrowth/en/);

Note: For patients less than 2 years old, growth charts are based on recumbent length instead of height, which is not collected in the study. As an approximation, height collected in the study is considered as equal to the recumbent length; for patients over 228 months- old, percentiles are not available and will be considered as missing.

The number and percentage of patients with notable vital sign values (high/low) will be presented by treatment group.

Vital signs shift table based on values classified as notable low, normal, notable high or notable (high and low) at baseline and worst post-baseline will be produced for pulse rate, diastolic BP and systolic BP. Baseline is defined as the last non-missing value prior to or coinciding with first dose. The worst post-baseline value refers to the worst post-baseline value on treatment.

Descriptive statistics (mean, median, standard deviation, minimum and maximum) will be tabulated for baseline, at each post-baseline time point and changes from baseline at each postbaseline time point for each vital sign measure. For each parameter, only patients with a value at both baseline and post baseline (on treatment) will be included.

A listing of all vital sign assessments will be produced by and notable values will be flagged. A separate listing of only the patients with notable vital sign values may also be produced. In the listing, the assessments collected outside of on-treatment period will be flagged.

2.8.4.3 Performance status

The Karnofsky and Lansky performance status scale (Table 2-16) will be used to assess physical health of patients:

PERFORMANCE STATUS CRITERIA Karnofsky and Lansky performance scores are intended to be in multiples of 10				
Karnofsky (age ≥16 years of age) Lansky (age <16 years)			/ (age <16 years)	
Score Description Score Description		Description		
100	Normal, no complaints no evidence of disease.	100	Fully active, normal.	
90	Able to carry on normal activity, minor signs of symptoms of disease.	90	Minor restrictions in physically strenuous activity.	
80	Normal activity with effort, some signs of symptoms of disease.	80	Active, but tires quickly.	

Novartis SAP	Confidential 30-Sep-2021 (6:19)		
70	Cares for self, unable to carry on normal activity or do active work.	70	Both greater restriction of and less time spent in play activity.
60	Requires occasional assistance, but is able to care for most of his/her needs.	60	Up and around, but minimal active play, keeps busy with quieter activities.
50	Requires considerable assistance and frequent medical care.	50	Gets dressed, but lies around much of the day; no active play, able to participate in all quiet play and activities.
40	Disabled, requires special care and assistance.	40	Mostly in bed, participates in quiet activities.
30	Severely disabled, hospitalization indicated. Death not imminent.	30	In bed, needs assistance even for quiet play.
20	Very sick, hospitalization indicated. Death not imminent.	20	Often sleeping; play entirely limited to very passive activities.
10	Moribund, fatal processes progressing rapidly.	10	No play, does not get out of bed.

[figure not shown]
Frequency counts and percentages of patients in the score category of 100, 90, 80, 70, and < 70 will be provided by time point based on the windows defined in Section 2.1.1. A summary of change from baseline by scheduled visits will be performed by treatment group, as well as the worst case post-baseline and the best case post-baseline changes during the study.

A supporting listing will also be provided.

Dermatological Evaluation 2.8.4.4

Skin examination results will be summarized by frequency counts and percentages of patients in each category (normal, abnormal) by scheduled time points by each treatment group. A supporting listing will also be provided.

2.8.4.7 Growth and development (Height and Weight)

Growth data consist of height, weight, BMI, height velocity and weight velocity.

Height and BMI will be summarized at 6-month intervals, using the standard deviation scores (SDS, also called z-score), velocity and velocity SDS. The relevant height and weight values for each 6-month period are defined using time windows, as defined in Table 5-3. The z-scores will allow identification of potential outliers.

The formula used to calculate the SDS and height and weight velocities are provided in the Appendix 5.3.2.

Note that BMI SDS are reported instead of weight SDS as no reference data for weight are provided by the WHO for age beyond 10.

Height and BMI SDS and height and weight velocity SDS will be summarized using descriptive statistics (mean, standard deviation, range) for each time window (at Baseline and thereafter allowing informal comparison of growth data), as well as by presenting number of patients with SDS values lower/higher than 5th/95th percentiles respectively.

Box plots will be plotted for each time window. A shift table to compare baseline SDS to the worst on-treatment SDS categorized as Low (SDS <- 1.645), High (SDS > 1.645) or Normal (- $1.645 \le SDS \le 1.645$) will be produced for height and BMI SDS. Another shift table to compare the baseline height SDS to the last available on-treatment height SDS categorized according to the main percentile lines (>95th, 95th to 90th, 90th to 75th, 75th to 50th, 50th to 25th, 25th to 10th, 10th to 5th and \le 5th percentile) will be produced. All height and BMI SDS, velocity and velocity SDS data will be listed, and values of SDS and velocity SDS outside of the central 95% of population values will be flagged as either High (SDS > 1.645) or Low (SDS <- 1.645).

Novartis	Confidential	Page 56
SAP	30-Sep-2021 (6:19)	CDRB436G2201

In addition, a mixed model will be used to estimate differences of change from baseline in height SDS between treatment groups. A mixed model with height SDS as the response variable and time, gender, and treatment as explanatory variables will be fit using PROC MIXED. See Appendix 5.4.5 for model specifications and further details.

2.8.4.8 Ophthalmologic exam

Visual acuity will be converted from snellen to logMAR scale as defined in Holladay 1997 ($\underline{20}$), and categorized as the following change from baseline:

- Improvement: $\geq 0.2 \log MAR$ improvement (decrease in logMAR)
- Stable: neither \geq 0.2 logMAR improvement nor worsening, where
- Worsening: $\geq 0.2 \log$ MAR worsening (increase in logMAR)

Visual acuity categories at each time point, as well as best and worst category on treatment will be presented. Further exploratory analyses of change in visual acuity may be performed. Data from ophthalmologic exams will be listed by treatment group.

2.8.4.10 Palatability

Data on palatability assessments for dabrafenib and trametinib oral solution (bitterness, sweetness, texture and overall taste) will be summarized and listed by treatment group.

2.8.4.11 Additional analyses

Time to first occurrence

Time to first occurrence of an event is defined as time from start of study treatment to the date of first occurrence of this event (or first event within an AE grouping), i.e. time in days is calculated as (start date of first occurrence of event) - (start of study treatment) +1.

For Kaplan-Meier analyses of time to occurrence, in the absence of an event during the ontreatment period, the censoring date applied will be **the earliest** of the following dates:

- death date
- new anticancer antineoplastic therapy start date
- end date of on-treatment period
- data cut-off date
- withdrawal of informed consent date.

Failure curves (ascending Kaplan-Meier curves) will be constructed. Median together with 95% confidence interval as well as 25th percentile and 75th percentile will be presented.

Novartis	Confidential	Page 57
SAP	30-Sep-2021 (6:19)	CDRB436G2201

In addition, the median time to occurrence for the subset of patients who experienced the event of interest will be calculated. Simple descriptive statistics, median, min and max as well as 25th percentile and 75th percentile, will be presented.

2.9 Pharmacokinetic endpoints

All PK analyses will be performed based on the PAS unless otherwise specified.

PK parameters

For subjects where dense PK is collected on Day 15, the PK parameters that will be determined if data permit are shown in Table 2-17. For subjects where sparse PK is collected, Ctrough and Cmax may be reported if data permit. The PK parameters will be derived using noncompartmental methods using WinNonlin[®] software version 6.4.

Table 2-17	Non-compartmental PK parameters for dabrafenib and trametinib
AUClast	The AUC from time zero to the last measurable concentration sampling time (tlast) (ng*h/mL)
AUCtau	The AUC calculated to the end of a dosing interval (tau) at steady-state (ng*h/mL); tau= 12 hrs
Cmax	The maximum (peak) observed plasma, blood, serum, or other body fluid drug concentration after single dose administration (ng/mL)
Tmax	The time to reach maximum (peak) plasma, blood, serum, or other body fluid drug concentration after single dose administration (h)
T1/2	The elimination half-life associated with the terminal slope (λz) of a semi logarithmic concentration-time curve (h).
Ctrough	Measured concentration at the end of a dosing interval at steady state (taken directly before next administration) (ng/mL)The trough (predose) plasma concentration determined directly from the raw concentration-time data
Cavg	Steady state average plasma concentration (ng/mL)
Tlast	The last measurable concentration sampling time for the AUClast calculation (h)

Descriptive statistics (n, mean, CV% mean, standard deviation (SD), median, geometric mean, CV% geo-mean, minimum and maximum) will be presented for Pharmacokinetic analysis set for all dabrafenib (and its metabolites) and trametinib PK parameters defined in Table 2-17, except Tmax and Tlast, where only n, median, minimum and maximum will be presented.

All individual PK parameters will be listed using the Full analysis set.

PK concentrations

Only valid PK concentrations will be used in the analyses as defined in Section 2.2.

Descriptive statistics (n, m (number of non-zero concentrations), mean, CV% mean, SD, median, geometric mean, CV% geo-mean, minimum and maximum) for dabrafenib, metabolites and trametinib concentrations will be presented by each scheduled time point and actual leading dose (i.e. the dose taken on the day prior to the PK sampling day) for the Pharmacokinetic analysis set. Zero concentrations will not be included in the geometric mean

Novartis	Confidential	Page 58
SAP	30-Sep-2021 (6:19)	CDRB436G2201

calculation. Graphical presentation will be provided on mean concentration at each scheduled time point for PK sub-population where the full PK profile is available.

Individual concentration-time profiles for dabrafenib and trametinib concentrations with median will be displayed graphically by treatment for Full analysis set on the semi-log view. In addition, the mean (+/- SD) and geometric mean concentration-time profiles for dabrafenib (+ its metabolites) and trametinib over time will be displayed graphically for Pharmacokinetic analysis set on the linear and semi-log view.

All individual plasma dabrafenib metabolites and trametinib concentration data will be listed for the Full analysis set.

Handling of PK data below LLOQ or missing

All concentration values below the lower limit of quantitation (LLOQ) are set to zero by the Bioanalyst, and will be displayed in the listings as zero and flagged. LLOQ values will be treated as zero in any calculations of summary statistics, and treated as missing for the calculation of the geometric means and their CV%. The number of non-zero concentrations will also be reported in the summary statistics.

Missing values for any PK data will not be imputed and will be treated as missing.

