2.9 Pharmacokinetic endpoints

PK analyses were performed at the time of primary analysis, at which time all data had already been collected. No further PK analysis will be performed for the Final CSR

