Summary of RDI will include categorical summaries based on clinically meaningful intervals (<50%, 50-<75%, 75-<90%, 90-<110%, >=110%.)Note that for the purposes of DI and RDI derivation only for carboplatin and vincristine, the last date of exposure for the duration of exposure component of this calculation will not consider death date.

DAR record number	Start/End Date	Dose Prescribed (mg) frequency	Dose Administere d (mg) [total daily]	Dose Changes, Dose Interruption ?	Dose Permanently Discontinued	Reason
1	01Jan2016 / 05Jan2016	125 mg BID	250	No	No	
2	06Jan2016 / 03Feb2016	125 mg BID	200	Yes	No	AE
3	04Feb2016 / 25Feb2016	130 mg BID	260	Yes	No	As per protoco

 Table 2-8
 Examples of dabrafenib dose administration and exposure

Duration of exposure (days) = 25Feb2016 - 01Jan2016 + 1 = 56 days

Planned cumulative dose (for 56 days) = 125*2*56 days = 14000 mg

Actual cumulative dose = 250*5 + 200*29 + 260*22 = 12770 mg

Dose intensity = 12770 mg / 56 days = 228.04 mg/day

Planned dose intensity = 14000 mg / 56 days = 250 mg/day

Relative dose intensity = DI / PDI = (228.04 mg/day) / (250 mg/day) = 91.2%

Table 2-9Examples of trametinib dose administration and exposure
--

DAR record number	Start/End Date	Dose Prescribed (mg), frequency	Dose Administere d (mg) [total daily]	Dose Changes, Dose Interruption?	Dose Permanently Discontinued	Reason
1	01Jan2016 / 10Jan2016	0.875 QD	0.875	No	No	

Novartis	Confidential	Page 31
SAP	30-Sep-2021 (6:19)	CDRB436G2201

DAR record number	Start/End Date	Dose Prescribed (mg), frequency	Dose Administere d (mg) [total daily]	Dose Changes, Dose Interruption?	Dose Permanently Discontinued	Reason
2	11Jan2016 / 15Jan2016	0.875 QD	0	Yes	No	AE
3	16Jan2016 / 25Feb2016	0.75 QD	0.75	Yes	No	AE

Duration of exposure = 25Feb2016 - 01Jan2016 + 1 = 56 days

Planned cumulative dose (for 56 days) = 0.875*56 days = 49 mg

Actual cumulative dose = 0.875*10 + 0*5 + 0.75*41 = 39.5 mg

Dose intensity = 39.5 mg / 56 days = 0.705 mg/day

Planned dose intensity = 49 mg / 56 days = 0.875 mg/day

Relative dose intensity = DI / PDI = (0.705 mg/day) / (0.875 mg/day) = 80.6%

Nominal Visit number	Start/End Date	Phase	Dose Prescribed (mg/m2), frequency	Dose Administ ered (mg) [total daily]	Dose Changes, Dose Interruption ?	Dose Permanently Discontinued	Reason
Week 1 Day 1	01Jan2016 / 01Jan2016	Induction	175 weekly	175	No	No	
Week 2 Day 1	08Jan2016 / 08Jan2016	Induction	175 weekly	0	Yes	No	AE

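### AUCtau is given one 12-hour tau for both drugs, although the same SAPs show trametinib dosed once daily, so tau needs to be stated per drug

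*SAP*

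**What the plan says.** Section 2.9 of LGG SAP Amendment 1 lists the parameters in Table 2-17, titled "Non-compartmental PK parameters for dabrafenib and trametinib". The AUCtau row reads "The AUC calculated to the end of a dosing interval (tau) at steady-state (ng*h/mL); tau= 12 hrs". It names no drug and makes no exception. The text below the table plans descriptive statistics "for all dabrafenib (and its metabolites) and trametinib PK parameters defined in Table 2-17", with only Tmax and Tlast given a reduced set of statistics, so trametinib AUCtau is a planned output. HGG SAP Amendment 2 has the same row in Table 2-14 and the same instruction.

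Section 2.4.1 of the same SAPs gives worked dosing examples (LGG Tables 2-8 and 2-9; HGG Tables 2-7 and 2-8). For dabrafenib, prescribed BID: "Planned cumulative dose (for 56 days) = 125*2*56 days = 14000 mg". For trametinib, prescribed QD: "Planned cumulative dose (for 56 days) = 0.875*56 days = 49 mg".

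The later SAPs for the final analysis do not revisit PK. The LGG one says "No further PK analysis will be performed for the Final CSR", and the HGG one says the same in other words. The 2021 tables are therefore the only PK parameter definitions in these documents.

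**The concern.** The AUCtau row defines the parameter by the end of a dosing interval and then fixes that interval at 12 hours for two drugs whose intervals differ in the same SAP. The table is also at odds with itself. Its Ctrough row is taken at the end of a dosing interval, just before the next administration. For a once-daily drug that is about 24 hours after the dose, while the AUCtau row ends the interval at 12.

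Characterising trametinib pharmacokinetics is a secondary objective in both cohorts. A half-interval area labelled AUCtau would be too low if set beside a full-interval AUC from once-daily dosing, and the label would not warn the reader.

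**Working it through.** **Step 1: dosing interval implied by the SAP's own arithmetic.** Interval = 24 h / doses per day, with doses per day read from the 56-day examples in section 2.4.1.

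- Dabrafenib: 125 × 2 × 56 = 14,000 mg, as stated. Two doses a day, so tau = 24/2 = 12 h. This reproduces the stated tau.
- Trametinib: 0.875 × 1 × 56 = 49 mg, as stated. One dose a day, so tau = 24/1 = 24 h. This does not match the stated tau. Twice-daily dosing would have given 0.875 × 2 × 56 = 98 mg.

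The 12-hour window covers 12/24 = 50% of the trametinib interval in time. No section of either SAP gives a 24-hour tau.

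**Step 2: what share of exposure falls in the first 12 hours.** Half the time is not half the exposure, and the documents give neither a half-life nor an absorption rate for trametinib. As an assumption, take a one-compartment oral model at steady state with a dose every 24 h, elimination rate ke = ln 2 / half-life and absorption rate ka. Up to a common constant:

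- AUC(0–24) = 1/ke − 1/ka
- AUC(0–12) = 1/[ke(1 + exp(−12ke))] − 1/[ka(1 + exp(−12ka))]

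Example, half-life 24 h and ka = 1 per hour: ke = 0.0289; AUC(0–24) = 34.62 − 1.00 = 33.62; AUC(0–12) = 20.28 − 1.00 = 19.28; share = 0.573.

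| Half-life (h) | ka 0.3 | ka 1 | ka 2 |
|---|---|---|---|
| 6 | 0.691 | 0.774 | 0.788 |
| 24 | 0.544 | 0.573 | 0.580 |
| 120 | 0.508 | 0.515 | 0.516 |

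Over the whole range tried, the share runs from 0.508 to 0.788. The understatement of AUCtau is 1 − share, so from 1 − 0.788 = 21% to 1 − 0.508 = 49%, in round terms 20 to 50%. It is largest when the half-life is long and the profile flat.

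**Step 3: Cavg.** The table gives no formula. If Cavg = AUCtau/tau with 12 h in both places, its ratio to the full-interval value is (AUC0–12 / 12) / (AUC0–24 / 24) = 2 × share. For a flat profile that is 2 × 0.5 = 1.0, no bias. Over the assumed range it is 2 × 0.508 = 1.02 to 2 × 0.788 = 1.58. Cavg would be unbiased or overstated, the opposite direction to AUCtau.

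**The case against.** The strongest reply is that the operative words are the end of a dosing interval, and that 12 hours is a carry-over from dabrafenib. A PK analyst could have applied 24 hours to trametinib without remark. The sampling windows are left to protocol section 7.2.3.1, which is not shown, and parameters are derived only where the data allow, so it is unknown whether a 0–24 h area was ever obtainable. The trametinib frequency is itself read from worked examples. The endpoint carries no test, alpha or sample size. AUClast, Cmax, Tmax, Ctrough, concentrations by time point and profile plots are planned as well, and none depends on a numeric tau.

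Much of this stands, and it limits the point. A reader might infer that reported trametinib exposure was in fact truncated, that it was halved, that Cavg was low too, or that the whole PK objective is compromised. The documents support none of these. They do not show which tau was used; half the interval in time is not half the area; Cavg would not be low under a consistent 12-hour tau; and the other exposure measures are untouched.

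What the reply does not remove is the conflict in the text. A stated numeric value governs both drugs and contradicts the once-daily arithmetic in the same document. That an analyst may have departed from it is a reason to check the output, not a substitute for a correct definition.

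**Conclusion.** The definition conflicts with the dosing frequency in the same SAPs, in both cohorts. Taken literally it makes trametinib AUCtau an AUC0–12. That this understates full-interval exposure needs no model, since any drug still present after 12 hours is left out. The 20 to 50% size is conditional on the one-compartment model and on the ranges chosen for half-life and absorption. The effect on Cavg is conditional on a formula that the SAPs do not give. The once-daily frequency comes from the SAPs' worked examples and should be confirmed against the protocol. The consequence is confined to a secondary, descriptive PK endpoint; ORR, its intervals and the sample size are not affected. It should be corrected because the correction is cheap and the label would otherwise mislead.

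**What to change.** - In Table 2-17 (LGG) and Table 2-14 (HGG), state tau per drug to match the frequencies already in the SAPs: 12 h for dabrafenib and its metabolites, 24 h for trametinib. This changes an analysis definition only, not any dose or schedule.
- State Cavg = AUCtau/tau with the same drug-specific tau.
- Because PK was reported at the primary analysis and is not repeated, check which tau produced the trametinib AUCtau and Cavg in those outputs. If it was 12 h, recompute both where sampling reaches the end of the interval; otherwise relabel the area as AUC0–12 and say over what period Cavg was averaged.
- Do not fill a missing 24-hour point with the pre-dose value. Section 2.9 of both SAPs says missing PK values are not imputed, so such a substitution would need that rule amended at the same time.

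The cost is the AUCtau and Cavg rows in two tables, one check of existing outputs and, at most, a rerun of two non-compartmental parameters for trametinib in the patients with dense Day 15 sampling.
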